5.1.1 Screening Assessments

All patients will be screened prior to registration. The following screening assessments will be performed within 28 days prior to trial entry unless stated otherwise (see section 7.3 for more details of the assessment):

- Demographic data
- Medical history (including prior diagnosis, treatment and any existing conditions)
- Height & Weight

Blood tests

- Full blood count and biochemistry (including glucose and if abnormal fasted glucose), Hba1c, triglycerides, cholesterol, Troponin (isoform as per institutional norm), serum creatinine, bilirubin, LDH and ALT/AST)
- Blood for virology. Patients must have negative virology for HIV and hepatitis C prior to trial entry. For stage one (AZD 2014 treatment only), hepatitis B serology must not indicate active infection. Prophylaxis is advised in patients who meet inclusion criteria 11 whilst being antihepatitis B sAg antibody positive and who are positive for anti-hepatitis B core antibody (with no surface antigen). Prophylaxis is not recommend for those with isolated anti-hepatitis B sAg and a history of vaccination.
- For stage 2 treatment (AZD 2014 with rituximab) Hepatitis B surface antigen and anti-core antibody must be negative.

Examinations/Tests

- Clinical assessment, including, vital signs (heart rate, systolic and diastolic BP, oxygen saturation (pulse oximetry), temperature, weight)
- ECOG performance status
- Assessment of constitutional symptoms -, night sweats, recurrent fever ≥38.0°C in the absence of infection, and history of weight loss.
- Urinalysis (test strip to include Haemoglobin, leukocytes, nitrite and proteins)
- Bone Marrow Trephine Biopsy (if indicated for disease staging)
- Pregnancy test for females of child-bearing potential (to be obtained prior to registration and within 7 days of starting therapy)
- Contraception review as per section 5.3 below

Radiology

• PET-CT (contrast enhanced CT component) Neck, Chest, Abdomen and Pelvis (NCAP) as per Torch PET manual. Contrast enhanced CT Neck, Chest, Abdomen and Pelvis (NCAP), can be performed at the same imaging session as the PET-CT if possible as per local practice. If performed at the same session, an unenhanced low dose CT should be performed

followed by a PET scan then a contrast enhanced CT NCAP so that accurate quantitation of PET data will be possible. A full inspiration breath-hold CT should be performed as part of the CT NCAP

• High resolution CT (HRCT) Chest to document the lung parenchyma status (if not captured during PET CT) in patients with symptoms or signs suggestive of parenchymal lung disease.

Cardiac assessments:

- Echocardiogram (Echo) including assessment of left ventricular end-systolic volume (LVESV), left ventricular end-diastolic volume (LVEDV) and LVEF.
- MUGA (if Echo cannot be performed) to assess LVEF

If an Echo cannot be performed, a MUGA scan to assess LVEF will be conducted. The modality of the cardiac function assessments must be consistent within patient, i.e., if Echo is used for the screening assessment then it should also be used for subsequent scans if required. The patient should also be examined using the same machine and operator throughout the study wherever possible. Other alternative methods of assessments could be used additionally if they are a part of the local standard of care, or if the Investigator considers them necessary for the therapeutic management of the patient. Important cardiac symptoms should be reported as AEs/serious AEs and should be carefully evaluated in regard to developing of acute or worsening of chronic cardiac failure, especially in anthracycline treated patients. Congestive cardiac failure should be treated and followed according to standard medical practice. An Echo/MUGA will also be carried out if a patient develops signs and/or symptoms suggestive of a deterioration in LVEF or in case of the pre-specified ECG finding such as T-wave inversions: (see the AZD2014 IB for more detailed explanation).

Samples for research

Blood and saliva samples should only be taken on a Monday, Tuesday or Wednesday due to the time taken to ship and process the samples on arrival at the laboratory.

- Blood sample collection for research
- Paraffin embedded tissue collection for research*
- Saliva sample at baseline for germline testing

*Tissue blocks from both initial diagnosis and relapse (if re-biopsy undertaken) will be collected. Rebiopsy at relapse is recommended if the patient's condition allows and there are no contraindications to biopsy. Refractory patients (or relapsed patients in whom re-biopsy is not possible) will be eligible for the study without re-biopsy provided initial diagnostic tissue is available and is within 3 months.

5.2 Informed Consent

It is the responsibility of the Investigator, as captured on the Site Signature and Delegation Log, to obtain written informed consent for each patient prior to performing any trial related procedure. A Patient Information Sheet (PIS) is provided to facilitate this process. Investigators must ensure that they adequately explain the aim, trial treatment, anticipated benefits and potential hazards of taking part in the trial to the patient. The Investigator should also stress that the patient is completely free to refuse to take part or withdraw from the trial at any time. The patient should be given ample time (e.g. 24 hours) to read the PIS and to discuss their participation with others outside of the site research team. The patient must be given an opportunity to ask questions which should be answered to their satisfaction. The right of the patient to refuse to participate in the trial without giving a reason must be respected.

If the patient expresses an interest in participating in the trial they should be asked to sign and date the latest version of the Informed Consent Form (ICF). The Investigator or designate must then sign and date the form. A copy of the ICF should be given to the patient, a copy should be filed in the hospital notes, and the original placed in the Investigator Site File (ISF). Once the patient is entered into the trial the patient's trial number should be entered on the ICF maintained in the ISF. In addition, if the patient has given explicit consent a copy of the signed ICF must be sent in the post to the Trials Office for review.

Details of the informed consent discussions should be recorded in the patient's medical notes, this should include date of, and information regarding, the initial discussion, the date consent was given,

with the name of the trial and the version number of the PIS and ICF. Throughout the trial the patient should have the opportunity to ask questions about the trial and any new information that may be relevant to the patient's continued participation should be shared with them in a timely manner. On occasion it may be necessary to re-consent the patient in which case the process above should be followed and the patient's right to withdraw from the trial respected.

The patient should be given ample time to read changes made to the patient information sheet, which may vary depending on the nature of the change and may re-consent at the same visit that new information is provided, if they wish to do so.

Electronic copies of the PIS and ICF are available from the Trials Office and should be printed or photocopied onto the headed paper of the local institution.

Details of all patients approached about the trial should be recorded on the Patient Screening /Enrolment Log and with the patient's prior consent their General Practitioner (GP) should also be informed that they are taking part in the trial. A GP Letter is provided electronically for this purpose.

5.3 Contraception

For patients receiving AZD2014 only

Females of and males with partners of childbearing potential must use adequate methods of contraception.

- *Females* of child-bearing potential to use 2 forms of contraception (1 highly effective method and 1 barrier method), from registration to 4 weeks after trial treatment discontinuation. Please note that use of oral, injected or implanted hormonal methods may not be highly effective as it is unknown if AZD2014 will reduce their effectiveness.
- *Males* should be surgically sterile or willing to use an effective method of barrier contraception and refrain from sperm donation from first treatment until 16 weeks after trial treatment discontinuation

For patients receiving rituximab

Contraception should be used from registration until at least 12 months following treatment discontinuation.

For patients to be classed as having evidence of non-child-bearing potential they must fulfill one of the following criteria at screening:

- Post-menopausal defined as amenorrhoeic for at least 12 consecutive months following cessation of all exogenous hormonal treatments. If under 50 Serum follicle-stimulating hormone (FSH) and luteinizing hormone (LH) levels must be in the postmenopausal range
- Documentation of irreversible surgical sterilisation by hysterectomy, bilateral oophorectomy or bilateral salpingectomy, but not tubal ligation

6. TRIAL ENTRY

Patients will be registered to the trial via the Cancer Research UK Clinical Trials Unit (CRCTU).

2:[name]

9am-5pm Monday to Friday

An eligibility checklist and registration form (found in the ISF) should be completed prior to registration by the Investigator or designee.

The patient trial number and treatment allocation will be given over the telephone, followed by a fax confirmation. Treatment should start within 7 days of registration.

7. TREATMENT DETAILS

7.1 Trial Treatment

7.1.1 Investigational Medicinal Product AZD2014

AZD2014 (vistusertib) is available for administration as a tablet for use in clinical trials. The oral tablet is presented as two strengths: 25 or 50 mg.

AZD2014 will be considered the IMP for the purposes of the trial. AZD2014 will be supplied free of charge for the trial by the manufacturers AstraZeneca.

AZD2014 doses can be taken with or without food at approximately the same time each morning and evening, 12 hours apart. Sugary and fatty foods should be avoided in the meals prior to taking a dose (see section 7.2 for further details).

Patients should avoid large amounts of grapefruit and Seville oranges (and other products containing these fruits, e.g. grapefruit juice or marmalade) during the study. No more than a small glass of grapefruit juice (120 mL) or half a grapefruit or 1 to 2 teaspoons (15 g) of Seville orange marmalade daily is allowed.

Patients should also avoid use of sun beds or tanning booths (including dye-based tanning booths) during the course of the study and for 3 months after the last dose. Use sunglasses and sun blocker (with SPF >30 to UVB and a high degree of protection against UVA) is advised, if exposed to sunlight during this period of time.

All study drug must be kept in a secure place under appropriate storage conditions. The IMP label on the bottle, the Investigators Brochure and the pharmacy manual specify the appropriate storage.

The IMP will be packaged and labelled in accordance with local regulations and Good Manufacturing Practice (GMP), stating that the drug is for clinical trial use only and to keep it out of the reach of children. For further instructions and ordering details, please refer to the pharmacy manual.

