4.2 Exclusion Criteria

Patients must not enter the study if any of the following exclusion criteria are fulfilled:

 Prior chemotherapy, biological therapy, radiation therapy, androgens, thalidomide, immunotherapy, other anticancer agents, and any investigational agents within 21days of registration (not including palliative radiotherapy at focal sites to non-target lesions). Corticosteroids are permitted during screening but should be weaned down to a maximum dose of prednisolone 10mg daily (or equivalent) by day 1 of cycle 1.

- With the exception of alopecia, any unresolved toxicities from prior chemotherapy should be no greater than CTCAE (Version 4.0) Grade 2 at the time of registration.

- 2. Major surgery within 4 weeks prior to entry to the study (excluding placement of vascular access), or minor surgery within 2 weeks of entry into the study.
- 3. Exposure to potent or moderate inhibitors or inducers of CYP3A4/5, Pgp (MDR1) and BCRP if taken within the stated washout periods before the first dose of study treatment. See Appendix 2.
- 4. Exposure to sensitive or narrow therapeutic range substrates of the drug transporters Pgp (MDR1), BCRP, MATE 1, MATE 2K, OATP1B1 and OATP1B3, within the appropriate wash-out period (a minimum of 5 x the reported terminal elimination half-life of each drug) before the first dose of study treatment. See table in appendix 3.
- 5. Previous treatment with any first generation mTORC1 inhibitors (rapamycin, sirolimus, temsirolimus, everolimus) or any dual mTORC1/2 inhibitors (e.g. AZD2014, AZD8055).
- 6. Patients who have experienced intolerable AEs prejudged by the treating Investigator due to other mTORC1 or mTORC1/2 inhibitors, PI3 kinase inhibitors, or AKT inhibitors.
- 7. Patients with proven central nervous system (CNS) involvement.
- 8. As judged by the Investigator, any evidence of severe or uncontrolled systemic diseases (e.g., severe hepatic impairment, interstitial lung disease (e.g.bilateral, diffuse, parenchymal lung disease), uncontrolled chronic renal diseases (e.g. glomerulonephritis, nephritic syndrome, Fanconi Syndrome or Renal tubular acidosis) or current unstable or uncompensated respiratory or cardiac conditions, or uncontrolled hypertension, active bleeding diatheses or active infection. Screening for chronic conditions is not required.
- 9. Patients who have experienced any of the following procedures or conditions currently or in the preceding 12 months:

- coronary artery bypass graft

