7.8.2 Other Concomitant Treatments

Information on any treatment pertinent to the inclusion/exclusion criteria in the 4 weeks prior to starting study treatment and all concomitant treatments given during the study with reasons for the treatment should be recorded. If medically feasible, patients taking regular medication, with the exception of potent or moderate inhibitors or inducers of CYP3A4/5 or CYP2C8, should be maintained on it throughout the study period.

- Patients who begin warfarin, or other vitamin K antagonists, therapy should be advised to have their anticoagulation monitored more frequently when receiving AZD2014 and should stop medication with AZD2014 at thrombocytopenia CTCAE Grade 3 or higher.
- Patients may continue to receive therapeutic bisphosphonates and erythropoietin preparations (e.g. Procrit, Epogen, Aranesp), if they were receiving them prior to beginning study treatment.
- Blood transfusions are allowed during the study.
- Other medication e.g. anti-emetics that are considered necessary for the patient's safety and well-being may be given at the discretion of the investigators.

Primary prophylaxis with anti-viral, anti-fungals and anti-Pneumocystis carinii pneumonia (*PCP*) medication are not required. These should be used according to local policy; however it should be noted that:

1. The systemic anti-Pneumocystis carinii pneumonia medication dapsone is **contraindicated** due CYP3A4/5 inhibitory effect.

2. Pentamidine **should NOT** be used for this indication due to its cardiac effects

Palliative radiotherapy to a site which does not contain a target lesion is permissible. Concomitant use of any other anticancer therapy, or moderate-to-significant inhibitors of CYP3A4 (Appendix 2), are prohibited.

Concomitant vaccination with live virus vaccines during rituximab treatment and for the duration the patient is peripherally depleted is prohibited.

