APPENDIX 2 – POTENT OR MODERATE INHIBITORS OR INDUCERS OF CYP3A4/5, PGP (MDR1) AND BCRP

Cytochrome P450 and transporter inhibitor/inducer restrictions		
CYP/ Transporter Category	Drugs	Minimum drug wash-out period
CYP3A4/5Strong Competitive inhibitors	grapefruit juice, indinavir, itraconazole, ketoconazole, nefazodone, nelfinavir, saquinovir, telithromycin and troleandomycin and voriconazole	1 week 2 weeks
	idelalisib	
CYP3A4/5 Strong Time dependent inhibitors	bocepravir, clarithromycin, cobicistat, danoprevir, elvitegravir, LCL161, lopinavir, mibefradil*, posaconazole, ritonavir, telaprevir and tipranivir	2 weeks
CYP3A4/5 Strong inhibitors (classification unknown)	conivaptan	1 week
CYP3A4/5 Moderate Competitive inhibitors	amprenavir, aprepitant, atazanavir, cimetidine, cyclosporine, fluconazole, imatinib and netupitant	1 week
CYP3A4/5 Moderate Time dependent inhibitors	ACT-178882, casopitant, crizotinib, darunavir, diltiazem erythromycin, ledipasvir, lomitapide, tofisopam and verapamil	2 weeks
	FK1706	half-life not found
CYP3A4/5 Moderate inhibitors (classification not known)	ciprofloxacin and dronedarone	1 week
	schisandra sphenanthera	half-life not found
CYP3A4/5 Strong inducers	carbamazepine, phenytoin, rifabutin, rifampicin and St. John's Wort	3 weeks
	enzalutamide and phenobarbital	5 weeks
	mitotane avasimibe	114 weeks half-life not found

Cytochrome P450 and transporter inhibitor/inducer restrictions		
CYP/ Transporter Category	Drugs	Minimum drug wash-out period
CYP3A4/5 Moderate inducers	bosentan, genistein, lersivirine, lopinavir, modafinil, nafcillin, ritonavir, semagacestat, , thioridazine and tipranavir	1 week
	etravirine efavirenz	2 weeks 3 weeks
Pgp (MDR1) inhibitors	talviraline dronedarone, erythromycin, indinavir, itraconazole,	half-life not found 1 week
	ketoconazole, lapatinib, lopinavir, ritonavir, quinidine and verapamil vorapaxer	10 weeks
	valspodar (PSC 833)	half-life not found
Pgp (MDR1) inducers	carbamazepine and rifampin	3 weeks
BCRP inhibitors	atazanavir, cyclosporine, lopinavir, ritonavir and tipranavir	1 week

APPENDIX 3 - SENSITIVE OR NARROW THERAPEUTIC RANGE IN VIVO SUBSTRATES OF THE DRUG TRANSPORTERSMATE, OATP & OCT

Transporter Substrate Restrictions

Transporters	Substrates
OATP (1B1 or 3)	bosentan, fexofenadine, glyburide, pitavastatin, pravastatin, repaglinide , rosuvastatin
MATE (1 or 2K)	cisplatin

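### Section 7.1.1 permits up to 120 mL of grapefruit juice a day on study, while Appendix 2 lists the juice as a strong CYP3A4/5 inhibitor and section 7.8.2 prohibits such inhibitors

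*Protocol*

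**What the plan says.** Five places in the protocol bear on grapefruit juice.

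- **Section 7.1.1 (AZD2014).** The dietary advice for the study period is about quantity: "Patients should avoid large amounts of grapefruit and Seville oranges". It then sets a daily ceiling: "No more than a small glass of grapefruit juice (120 mL"), with separate limits for the whole fruit and for Seville orange marmalade. Intake up to that ceiling is expressly permitted.
- **Appendix 2.** The row labelled "CYP3A4/5Strong Competitive inhibitors" begins with "grapefruit juice, indinavir, itraconazole, ketoconazole". No amount is attached to the juice. The row carries a minimum wash-out.
- **Section 7.8.2.** Under concomitant treatments, "moderate-to-significant inhibitors of CYP3A4 (Appendix 2), are prohibited".
- **Section 7.8.1.** If a patient needs a restricted CYP3A4/5 inhibitor for a short time, AZD2014 is withheld for three days beforehand and restarted only after the Appendix 2 period has passed.
- **Section 4.2, exclusion criterion 3** (also in the synopsis). Entry is barred by "Exposure to potent or moderate inhibitors or inducers of CYP3A4/5, Pgp (MDR1) and BCRP if taken within the stated washout periods" before the first dose, with a pointer to Appendix 2.

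**The concern.** The same named product is allowed every day in one section and falls in a prohibited class in another. Section 7.1.1 does not mention Appendix 2. Appendix 2, 7.8.1, 7.8.2 and exclusion criterion 3 do not mention 7.1.1.

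A site working from 7.1.1 would tell a patient that a small daily glass is acceptable. A site working from Appendix 2 and 7.8.2 would tell the same patient that it is prohibited, and would record it as a deviation. Patients in one small trial could then receive different instructions on an interacting product, and a deviation listing would partly reflect which page each site had read.

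**Working it through.** No figure in the plan depends on this point, so there is no power or error rate to reproduce. The check sets the passages side by side and makes two short comparisons of days.

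**Step 1: is it the same product?** Yes. Section 7.1.1 and Appendix 2 both name grapefruit juice. The other items in 7.1.1 (half a grapefruit, Seville orange marmalade) do not appear in Appendix 2, so the direct conflict is confined to the juice.

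**Step 2: does the 7.8.2 prohibition reach it?** Section 7.8.2 covers moderate-to-significant CYP3A4 inhibitors and refers to Appendix 2 for what those are. Appendix 2 places the juice in a strong class, which is above moderate. The juice is therefore inside the prohibition as written.

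**Step 3: does quantity resolve it?** Section 7.1.1 turns on quantity (120 mL). Appendix 2 and 7.8.2 give no quantity below which the listing does not apply.

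**Step 4: does the dosing schedule resolve it?** The row shows two wash-out values, 1 week and 2 weeks. The natural reading gives 1 week to the group that starts with grapefruit juice and 2 weeks to idelalisib, which stands apart on its own line. Section 7.2 gives AZD2014 on 2 consecutive days each week:

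- treatment-free gap = 7 − 2 = 5 days
- wash-out = 7 days (or 14 on the other reading)
- 5 < 7 (and 5 < 14)

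Even a single glass at the start of the gap could not be washed out before the next scheduled dose, and daily juice leaves no juice-free interval at all. The conflict does not depend on which value is right, because 7.8.2 prohibits concomitant use whatever the wash-out.

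**Step 5: the neighbouring rules.**

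- *Exclusion criterion 3* concerns exposure before the first dose. The 7.1.1 allowance is worded for the study period and sits under treatment details. Read literally, juice in the week before dosing excludes a patient who may drink it daily once dosed.
- *Section 7.8.1* is worded for a patient who needs a restricted inhibitor for a short time. Whether that covers juice taken as food is not stated. If it did, one glass would imply at least 3 + 7 = 10 days without AZD2014. That is longer than the 5-day gap, so scheduled doses would be missed.

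**The case against.** The best reply is that 7.1.1 is the only text dealing with grapefruit as food and by amount. On that view it is the specific rule, and Appendix 2 is a general interaction list for medicines. A sensible site might read it so. This makes the conflict less disruptive in practice but does not remove it: Appendix 2 lists the juice by name, gives it a wash-out and states no amount, and no sentence makes 7.1.1 an exception.

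Three stronger readings are tempting, and the documents do not support them.

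- **That a patient who follows 7.1.1 breaches every related rule.** Exclusion criterion 3 looks at intake before the first dose, so drinking juice on treatment does not breach it. Section 7.8.1 speaks of a needed short-term administration, which does not plainly describe diet. These two rules are left unclear. The direct contradiction is with 7.8.2 through Appendix 2.
- **That everything in Appendix 2 is banned outright.** Section 7.8.1 provides for short-term inhibitor use with AZD2014 withheld, and says that short-term inducers may be permitted.
- **That a hold of AZD2014 because of juice would count against the tolerability endpoint.** Section 12.6 counts toxicities that lead to treatment delays or dose modifications in the first 2 cycles. A precautionary hold without toxicity is not such an event, so the conflict has no demonstrated route into the tolerability decision.

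**Conclusion.** The inconsistency is real and is wrong as written. Section 7.1.1 permits up to 120 mL of grapefruit juice daily on study, and Appendix 2 with 7.8.2 prohibits the same product at any amount. The standing of the juice under exclusion criterion 3 and 7.8.1 is unclear as a consequence.

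Its size cannot be stated. The protocol gives no data on AZD2014 exposure with grapefruit juice, so any effect on toxicity would be guesswork. The primary analysis, sample size and error rates are untouched. The point is minor: it concerns consistent patient instructions, safety and the recording of deviations.

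The conclusion assumes that the juice in Appendix 2 is meant without a quantity limit, since none is given, and that a strong inhibitor falls within the 7.8.2 wording. It does not depend on whether the wash-out is 1 or 2 weeks.

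**What to change.** The sponsor, with its clinical pharmacology advice, should reconcile section 7.1.1 with Appendix 2, 7.8.1, 7.8.2 and exclusion criterion 3 (section 4.2 and the synopsis), so that grapefruit juice carries one rule throughout. The amended text should settle three things:

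- how juice is treated during treatment;
- whether intake before the first dose bears on eligibility;
- whether 7.8.1 applies to juice taken as food.

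If a dietary allowance is intended as an exception, each of these places should say so. If not, 7.1.1 should be brought into line with the others. This review does not say which is right. The patient instructions should carry the same rule.

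The cost is a wording amendment, with no change to design, sample size or analysis.
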